# ional Withholding of Amgen Investigational

#### 6.3.2 Criteria for Conditional Withholding of Amgen Investigational Product and Other Protocol-required Therapies Due to Potential Hepatotoxicity

For subjects who do not meet the criteria for permanent discontinuation of Amgen IP outlined above and have no underlying liver disease, and eligibility criteria requiring normal transaminases and TBL at baseline or subjects with underlying liver disease and baseline abnormal transaminases, the following rules are recommended for withholding of Amgen IP and other protocol-required therapies:

	5 5
Baseline AST or ALT value	AST or ALT elevation
Any	> 8 × ULN at any time
Any	> 5 × ULN but < 8 × ULN for $\ge$ 2 weeks
Any	> 5 × ULN but < 8 × ULN and unable to adhere to enhanced monitoring schedule
Any	> 3 × ULN with clinical signs or symptoms that are consistent with hepatitis (such as right upper quadrant pain/tendemess, fever, nausea, vomiting, jaundice).

• Elevation of either AST or ALT according to the following schedule:

- OR: TBL > 3 × ULN at any time
- OR: ALP > 8 × ULN at any time

Cinacalcet should be withheld pending investigation into alternative causes of DILI. If investigational product(s) is withheld, the subject is to be followed according to recommendations in Appendix A for possible DILI. Rechallenge may be considered if an alternative cause for impaired liver tests (ALT, AST, ALP) and/or elevated TBL, is discovered and the laboratory abnormalities resolve to normal or baseline (Section 6.3.3).

## 6.3.3 Criteria for Rechallenge of Amgen Investigational Product and Other Protocol-required Therapies After Potential Hepatotoxicity

The decision to rechallenge the subject should be discussed and agreed upon unanimously by the subject's legally acceptable representative(s), investigator, and Amgen.

If signs or symptoms recur with rechallenge, then cinacalcet should be permanently discontinued. Subjects who clearly meet the criteria for permanent discontinuation (as described in Section 6.3.1) should never be rechallenged.

Page 40 of 79

CONFIDENTIAL

# **AMGEN**®

#### 6.4 Concomitant Therapy

Throughout the study, investigators may prescribe any concomitant medications or treatments deemed necessary to provide adequate supportive care except for those listed in Section 6.6.

Vitamin D sterols, calcium supplementation, and/or phosphate binders should be administered as appropriate per individual clinic practice.

Dialysate calcium concentrations should not be adjusted during the course of the trial, remaining at  $\geq$  2.5 mEq/L.

All concomitant medications taken by a subject while on study are to be recorded on the eCRF. Refer to Section 7.3.7 for additional information regarding what is to be recorded.

## 6.5 Product Complaints

A product complaint is any written, electronic, or oral communication that alleges deficiencies related to the identity, quality, durability, reliability, safety, effectiveness, or performance of any investigational or non-investigational product(s) or device(s).

Any product complaint(s) associated with an investigational product(s) or non-investigational product(s) or device(s) supplied by Amgen are to be reported according to the instructions provided in the IPIM.

#### 6.6 Excluded Treatments and/or Procedures During Study Period

Subjects are prohibited from participating in other interventional studies (eg, studies which require medical device use or drug therapy or with protocol-required procedures) while participating in this study.

Cinacalcet is not approved for use in children and the use of commercial cinacalcet while participating in this study is prohibited. Refer to Section 7.3.7 for additional information regarding the reporting of commercial cinacalcet use.

Subjects should not receive any medications known to prolong the QT interval (eg, ondansetron, albuterol) while participating in this study. In addition, the use of grapefruit juice, herbal medications, CYP3A4 inhibitors (eg, erythromycin, clarithromycin, ketoconazole, itraconazole), or CYP2D6 substrates (eg, flecainide, propafenone, metoprolol, desipramine, nortriptyline, clomipramine) are excluded during the study. If subjects require these medications for temporary use, the administration of cinacalcet is to be withheld until the concomitant medication has been discontinued, at which time

Page 42 of 79

cinacalcet administration can be resumed. Additional information may be found in the IPIM.

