#### 6.2.3.1.1.1 Dosage Adjustments

The initial dose of cinacalcet and all subsequent doses will be calculated by the site staff and confirmed by the IVR/IWR system. Subjects from the SOC arm will start at the initial cinacalcet dose of 0.20 mg/kg/day, based on the subject's dry weight at day 1 of Study 20140159, rounded down to the lowest PSD.

Subjects from the cinacalcet arm with  $\leq$  14 days between the last dose of cinacalcet treatment in Study 20130356 and day 1 of Study 20140159 will start cinacalcet dosing at the same dose they received at the completion of the EOIP visit and follow weekly dose adjustment based on the Table 1. For subjects from the cinacalcet arm with > 14 days between the last dose of cinacalcet treatment in Study 20130356 and day 1 of

AMGEN

Page 26 of 79

Page 27 of 79

Study 20140159, the initial dose of cinacalcet will be 0.20 mg/kg/day, based on the subject's dry weight at day 1 of 20140159, rounded down to the lowest PSD, will be assigned.

Dose adjustments for subjects receiving cinacalcet will be assessed at each weekly visit during the treatment period. The daily dose of cinacalcet may only be increased at monthly titration visits (week 4, 8, 12, 16, 20, and 24); it can't be increased at any other time during the treatment period. At all weekly visits (including week 4, 8, 12, 16, 20, and 24), the dose may be maintained, reduced or withheld based upon the dose adjustment criteria in Table 1.

If any of the criteria for dose withholding are met at any time during the trial, including between scheduled study visits (ie, unscheduled), the dose of cinacalcet is to be withheld until all of the following criteria are met:

- central laboratory corrected calcium value is >8.4 mg/dL
- iPTH is > 150 pg/mL
- ionized calcium is >1.05mmol/L
- subject has no symptoms of hypocalcemia
- subject doesn't have any ongoing adverse event(s) which warrant withholding of cinacalcet.

If a subject dose is being withheld, ionized calcium levels should be assessed weekly until an ionized calcium of >1.05 mmol/L is obtained, at which point, cCa and iPTH should be assessed by the central laboratory.

Once all the restart criteria above are met, cinacalcet may be restarted at one PSD below the previous dose received. Subjects receiving the lowest PSD (2.5 mg) who require a dose reduction will have their dose withheld until the criteria for maintaining or increasing the dose are met, at which time they will restart dosing at 2.5 mg/day.

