If subjects require temporary administration of concomitant medications that are known to prolong the QTc interval, are CYP3A4 inhibitors, or are CYP2D6 substrates, the administration of IP is to be withheld. The dose may be restarted at one PSD below the previous dose once the treatment with the concomitant medication has completed and all of the restart criteria above are met.

If IP has been withheld or missed for > 14 days, the subject will resume dosing at the starting dose level once (initial dose in parent Studies 20130356 or 20110100) all restart criteria are met based on dry weight at day 1 of Study 20140159.

AMGEN

Page 28 of 79

If any of the criteria for dose decrease are met between scheduled study visits, the dose of cinacalcet is to be suspended until the next visit at which time the dose will be decreased per dose adjustment procedures of that visit.

CONFIDENTIAL

Product: Cinacalcet HCI Protocol Number: 20140159 Date: 01 June 2016 Page 29 of 79

	Monthly Dose Titration Visit Rules (Weeks 4, 8, 12, 16, 20, 24)				Weekly Dose Adjustment Visit Rules (Weeks 1, 2, 3, 5, 6, 7, 9, 10, 11, 13, 14, 15, 17, 18, 19, 21, 22, 23, 25, 26, 27)			Dose Withholding for Safety at Any Time (Monthly, Weekly or Unscheduled)
	↑ one PSD	Maintain Dose	↓ one PSD**	withhold*	Maintain Dose	↓ one PSD**	withhold*	withhold*
	(if all c riteria met)	(if al l criteria met)	(if any criteria met)	(if any criteria met)	(if al l criteria met)	(if any criteria met)	(if any criteria met)	(if any criteria met)
Corrected Calcium (central laboratory)	≥ 8.4 mg/dL	≥8.4 mg/dL	≥ 8.0 - < 8.4 mg/dL	< 8.0 mg/dL	≥ 8.4 mg/dL	≥ 8.0 - < 8.4 mg/dL	< 8.0 mg/dL	< 8.0 mg/dL
	(≥ 2.1 mmol/L)	(≥2.1 mmol/L)	(≥ 2.0- < 2.1 mmol/L)	(< 2.0 mmol/L)	(≥ 2.1 mmol/L)	(≥ 2.0- < 2.1 mmol/L)	(< 2.0 mmol/L)	(< 2.0 mmol/L)
Ionized Calcium	≥ 1.05 mmol/L	≥ 1.05 mmol/L	≥ 1.00 - < 1.05 mmol/L	< 1.00 mmol/L	≥ 1.05 mmol/L	≥ 1.00 - < 1.05 mmol/L	< 1.00 mmol/L	< 1.00 mmol/L
Total Calcium (local laboratory)	N/A	N/A	N/A	< 8.0 mg/dL (< 2.0 mmol/L)	N/A	N/A	< 8.0 mg/dL (< 2.0 mmol/L)	< 8.0 mg/dL (< 2.0 mmol/L)
iPTH	≥ 300 pg/mL	≥ 150 - < 300 pg/mL	≥ 100 - < 150 pg/mL	< 100 pg/mL	≥ 150 pg/mL	≥ 100 - < 150 pg/mL	< 100 pg/mL	< 100 pg/mL
	(≥ 31.8 pmol/L)	(≥ 15.9 - < 31.8 pmol/L)	(≥ 10.6 - < 15.9 pmol/L)	(< 10.6 pmol/L)	(≥ 15.9 pmol/L)	(≥ 10.6 - < 15.9 pmol/L)	(< 10.6 pmol/L)	(< 10.6 pmol/L)
Symptoms of Hypocalcemia	None	None	N/A	Yes	None	N/A	Yes	Yes

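### After temporary use of a prohibited medicine, Protocol Section 6.6 lets cinacalcet resume with fewer conditions than Section 6.2.3.1, names no dose, and does not refer to that section

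*Protocol*

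**What the plan says.** **Protocol Section 6.6** excludes QT-prolonging drugs, grapefruit juice, herbal medications, CYP3A4 inhibitors and CYP2D6 substrates. For temporary use, "the administration of cinacalcet is to be withheld until the concomitant medication has been discontinued, at which time", and then "cinacalcet administration can be resumed. Additional information may be found in the IPIM". The only pointer is to the Investigational Product Instruction Manual (IPIM).

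**Protocol Sections 6.2.3.1.1.1, 6.2.3.1.2.1 and 6.2.3.1.2.2** cover the same event for QTc-prolonging drugs, CYP3A4 inhibitors and CYP2D6 substrates. Each says "The dose may be restarted at one PSD below the previous dose", and only "once the treatment with the concomitant medication has completed and all of the restart criteria above are met". In Section 6.2.3.1.1.1 the criteria include "central laboratory corrected calcium value is >8.4 mg/dL" and "iPTH is > 150 pg/mL", ionized calcium above 1.05 mmol/L, no symptoms of hypocalcemia and no ongoing adverse event that warrants withholding. The other two sections have the same structure. Below 2 years the calcium limits are 9.0 mg/dL and 1.13 mmol/L.

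**More than 14 days off drug.** The same three sections send the subject back to the starting dose. The paragraph after Table 3 repeats this for more than 14 consecutive missed doses and expressly includes withholding for a concomitant medication.

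**The concern.** One event has two current rules. Section 6.4 sends investigators to Section 6.6 for the medicines they may not use, so a site handling a prohibited medicine has reason to read that section. What it finds there is one condition for resuming.

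The event is foreseeable. Section 2.4 lists nausea and vomiting among the most common adverse events, and ondansetron is one of the protocol's own examples of a prohibited drug. Hypocalcemia and QT prolongation are events of interest in the primary endpoint (Section 10.4.2). Section 2.4 also reports a pediatric death in the presence of severe hypocalcemia in which a role of cinacalcet could not be excluded. With about 60 sites (Section 3.2), two children with the same short course of a prohibited drug could restart under different conditions and possibly at different doses. That affects subject safety first, and then the comparability of exposure behind the descriptive safety summaries.

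**Working it through.** The plan gives no figure to reproduce. The check is a comparison of texts plus simple dose ratios.

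**1. The two rules side by side**

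| Element | Section 6.6 | Sections 6.2.3.1.1.1, 6.2.3.1.2.1, 6.2.3.1.2.2 |
|---|---|---|
| Prohibited medicine stopped | Required | Required |
| Central corrected calcium, iPTH, ionized calcium | Not mentioned | All required |
| No symptoms; no adverse event warranting withholding | Not mentioned | Both required |
| Dose on restart | Not stated | One PSD below the previous dose |
| More than 14 days off drug | Not mentioned | Initial dose |
| Grapefruit juice, herbal medications | Covered | Not named in the concomitant-medication paragraphs |
| Reference to the other section | None | None |

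The conflict is over conditions and timing. On dose, Section 6.6 is silent.

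**2. What a site following Section 6.6 alone could miss**

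- *Still in force:* weekly ionized calcium through week 28 (Synopsis); no new bottle without an ionized calcium value (Section 6.2.3); withholding at any time under Tables 1 to 3; IVR/IWR confirmation of doses (Section 6.2.3.1).
- *Not secured:* the restart-specific corrected calcium, iPTH and symptom criteria. In Table 4, iPTH is scheduled at weeks 3, 7, 11, 15, 19, 23 and 28, so the gaps are 4 weeks and then 28 − 23 = 5 weeks. Corrected calcium follows the same pattern after week 3.
- *Thresholds differ:* in Tables 1 and 3, any-time withholding starts at corrected calcium below 8.0 mg/dL, ionized calcium below 1.00 mmol/L or iPTH below 100 pg/mL, while restart needs values above 8.4, 1.05 and 150. In Table 2 the pairs are 8.6 and 9.0, 1.08 and 1.13, and 100 and 150. Values between the paired limits fail restart without triggering withholding, so the withholding rules do not replace the restart criteria.
- *Between visits:* drug already at home could be resumed on the day the other medicine stops.

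**3. Dose ratios**

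Inputs are the PSD lists in Section 6.2.3. The ratio is each dose divided by the next lower dose. It measures the difference only if a site takes resumption to mean the previous dose, which Section 6.6 does not say.

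- From 6 years (2.5, 5, 10, 15, 30, 60, 90, 120, 180 mg): 2.0, 2.0, 1.5, 2.0, 2.0, 1.5, 1.33, 1.5. The range is 1.33 (120/90) to 2.0 (for example 60/30).
- Below 6 years (1, 2.5, 5, 7.5, 10, 15, 30, 60 mg): 2.5, 2.0, 1.5, 1.33, 1.5, 2.0, 2.0. The range is 1.33 (10/7.5) to 2.5 (2.5/1).
- At the lowest PSD the dosing sections restart at that same dose, so there is no difference.

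After more than 14 days the comparator is the initial dose, and these ratios do not apply. No duration follows either: increases are allowed only at weeks 4, 8, 12, 16, 20 and 24, and only if all criteria are met, while reductions can happen weekly.

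**The case against.** The best defense is that the protocol says where restart rules live. Sections 3.1.1 and 3.1.2 say that dosing follows the restarting rules of Section 6.2.3 and Section 6.2.3.1.2 respectively, and SAP Section 3.1.2 repeats the reference to Section 6.2.3. Section 6.6 is a list of exclusions, its wording is permissive, and a site that follows Section 6.2.3.1 breaches nothing in it. It can be read as a shorter statement of the same rule, and the IPIM, which is not available here, may say more.

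Much of this stands, and it limits the point to an inconsistency of wording. It does not remove it. Section 6.6 ties resumption to the moment the other medicine is discontinued, which reads as sufficient in itself, and nothing there sends the reader to Section 6.2.3.1. Section 6.2.1 describes the IPIM as covering storage, preparation and administration. The Amendment 2 rationale says restart criteria were made consistent for all holds, which suggests an oversight in Section 6.6 and not a deliberate exception.

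Stronger readings are tempting, and the documents do not support them:

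- *That subjects could restart with no calcium check at all.* Weekly ionized calcium and the dispensing rule apply whichever section is followed. A restart with no check at all is plausible only between visits.
- *That the sections prescribe different doses.* Section 6.6 prescribes none.
- *That site dosing is uncontrolled.* IVR/IWR confirms doses, although the documents do not show which restart rule it applies or whether it governs resumption between visits.
- *That one step lower is the rule in every case.* After more than 14 days off drug it is the initial dose.

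**Conclusion.** The inconsistency is real and in current text. Section 6.6, followed as written, omits the restart-specific criteria, the dose level and the more-than-14-day case that the dosing sections set for the same event. It also covers two product types to which those paragraphs do not clearly extend.

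The possible dose difference is 1.33 to 2.0 times from 6 years and 1.33 to 2.5 times below 6 years. It rests on the assumption that a site takes resumption to mean the previous dose, and it is nil at the lowest PSD. The documents give no frequency for temporary use of prohibited medicines, so the effect on hypocalcemia or QT events cannot be sized. A reader might infer that the primary endpoint is materially distorted, but nothing in the documents shows that. Both rules also require the interacting medicine to be stopped first. No sample size or error rate is affected. The point should be corrected because it bears on subject safety and is cheap to fix.

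**What to change.** Reconcile Section 6.6 with Sections 6.2.3.1.1.1, 6.2.3.1.2.1 and 6.2.3.1.2.2 and with the paragraph after Table 3, so that a single restart rule covers temporary use of a prohibited medicine. It should state:

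- the conditions for restart;
- the dose level;
- what happens after more than 14 days off drug;
- which products trigger it, including whether grapefruit juice and herbal medications do.

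Replace the resumption sentence in Section 6.6 with a reference to that rule, and check that the IVR/IWR logic and the IPIM agree with it. The sponsor's clinical team must decide which rule stands; this review takes no view on that.

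The cost is about one sentence in Section 6.6 at the next amendment, matching wording in the dosing sections where needed, and a memo to sites. No procedures are added.

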# 7. STUDY PROCEDURES

# 7.1 Schedule of Assessments

Screening assessments and study procedures required for each visit are outlined in this section and the Schedule of Assessments (Table 4). The informed consent, and assent if applicable, must be obtained prior to performing any screening or study procedures.

CONFIDENTIAL

AMGEN

Product:	Cinacalcet HCI								
Protocol	Number:	20140159							
Date: 01	June 201	6							

							٦	a b	le 4	I. S	Sch	edı	lle	of /	١ss	ess	me	nts	;												
	Screening							Treatment Period (Week)																FU F	Period						
	Week -1	7	1	2	3	4	5	6	7	8	9	10	11	12	13	14	15	16	17	18	19	20	21	22	23	24	25	26	27	EOIP W28	ET/EOS W32
GENERAL & SAFETY A	SSESSMENT	s																					-	-		-		-			
Informed consent,	×																														
Assent (if applicable)	X																														
Medical/Surgical History		Х																													
12-lead ECG		Х																												X	Х
Physical Exam		X 																													X
Height, Tanner Stage		X 																													X
Dry Weight		X 																													Х
Dialysate Ca																															
Concentration		X																													
Blood Pressure, Heart		X 	1		x				x				x				v				v				v				x	x	×
Rate		X			×				×				×				X				X				X				×	×	X
Concomitant	X 		_												0															V	V
Medications 	~												Re	ecord	Cor	tinuc	usiy													X	X
Patient Diary Review		X1	X	X	X	X	X	X	X	X	X	X	X	X	Х	X	X	X	Х	X	X	X	X	X	X	X	X	X	X	Х	
Adverse events 			_										R	ecor	d Co	ntinu	ously	,												X	Х
Serious Adverse events 													R	ecor	d Co	ntinu	ously	/												Х	Х
LABORATORY ASSESS	MENTS																														
Ionized Ca		X	X	X	X	X	X	X	X	X	X	X	X	X	Х	X	X	X	Х	X	X	X	X	X	X	X	X	X	Х	Х	
Liver Function Tests	X 	Х											X												X						Х
Chemistry, hematology, 25(OH)Vit D 	X 	X 																												х	X
Ca, Albumin, cCa, P	X 	X 	X		X				X				X				X				X				X					X	Х
iPTH	X 	X1		1	X				X		-		X				X				X				X	1	-	1		X	X
Total & Bioavail Testosterone (male)		X 1																												x	
Serum Pregnancy Test (females of child bearing	х																														x
potential) BIOMARKER ASSESSM	ENTS																														
BALP, NTx, CTx, P1NP, FGF 23 		X 1																												х	
DOSING	1	·		1	-	1	1	1	1	1		-			1	1												-			
Dispensing		X	X	X	X	X	X	X	X	X	X	X	X	X	X	X	X	X	Х	X	X	X	X	X	X	X	X	X	X		
Cinacalcet Dose		v	1	-		v				v	1	1		v				v				v				v		1			
Titration Footpotes defined on next		X				X				X				X				х				X				X					

Footnotes defined on next page

CONFIDENTIAL

# AMGEN'

Page 43 of 79

Page 45
---------

Product	Cinacalcet HCI										
Protoco	I Number:	20140159									
Date: 0	1 June 201	6									

Page 44 of 79

Note: When it is not possible to perform a study visit at the specified time point, the visit may be performed within ± 3 days.

1 - Where the Screening and day 1 assessments for Study 20140159 overlap with visits in the Studies 20130356 or 20110100, these will be performed once at the site and applied to both study visits to minimize duplicate study assessments.

2 - These procedures are required for Study 20140159 screening visit if > 14 days since last study visit in Studies 20130356 or 20110100 for subjects impacted by study termination. 3 - Biomarker Assessments and 25 (OH) Vit D are not required for subjects previously enrolled in 20110100. If baseline FGF23 is not collected at day 1, it must not be collected at week 28.

Refer to the applicable supplemental laboratory manuals for detailed collection and handling procedures.

#### 7.2 General Study Procedures

All on-study visits and dosing should be scheduled from day 1. Week 1 begins one week after the day 1 visit. It is important to perform study assessments and obtain samples at the time points outlined in the Schedule of Assessments in Section 7.1.

The duplicate study assessments will be collected once for both studies as described in Section 7.2.2.

When it is not possible to perform a study visit at the specified time point, the visit may be performed within  $\pm$  3 days. If a study visit is missed, subsequent visits should resume on the original visit schedule. Missed assessments at prior visits should not be duplicated at subsequent visits.

With the exception of screening assessments, all study procedures for a visit must be completed on the same day.

It is the responsibility of the investigator to ensure that all procedures are performed according to the protocol.

Any blood or serum collected according to the Schedule of Assessments may be analyzed for any of the tests outlined in the protocol and for any tests necessary to ensure subject safety. This includes testing to ensure analytical methods produce reliable and valid data throughout the course of the study. This may also include, but is not limited to, investigation of unexpected results, incurred sample reanalysis, and analyses for method transfer and comparability.

Details regarding each type of procedure are provided in Section 7.3

# 7.2.1 Screening and Enrollment

The following procedures are to be completed during the screening period at time points designated in the Schedule of Assessments (Section 7.1, Table 4):

- Confirmation that the Informed Consent Form and Assent Form (if applicable)
   have been signed
- Registration of the subject in the IVR/IWR system
- Serum pregnancy test
- Serum calcium, serum albumin, and calculation of cCa, phosphorus
- iPTH

# 7.2.2 Day 1

The following day 1 procedures are also required for the EOIP study visit for Amgen Study 20130356 and End of Study visit for Study 20110100 except where indicated. These procedures should not be duplicated and may be collected once where study visits overlap and entered onto the appropriate eCRF once eligibility for this study has been confirmed:

- 12-lead ECG
- physical exam
- dry weight
- height/Tanner stage
- dialysate calcium, type of dialysis
- blood pressure, heart rate
- ionized calcium
- central laboratory assessments including the following
  - $\circ$   $\,$  serum calcium, serum albumin, and calculation of cCa, phosphorus  $\,$
  - o iPTH
  - liver Function Tests (LFT)
  - o chemistry panel
  - o hematology panel
  - 25 (OH) Vitamin D (not required for subjects from 20110100)
  - o total & bioavailable testosterone (male)
  - bone specific alkaline phosphatase (BALP), cross-linked N-telopeptides of type 1 collagen (NTx), type 1 collagen cross-linked telopeptide (CTx), amino terminal propeptide of type 1 collagen (P1NP), FGF23 (not required for subjects from 20110100).

The following day 1 procedures will be recorded on the day 1 eCRF:

- medical history (including ongoing AEs/SAEs from studies, 20130356 and 20110100)
- concomitant medications
- adverse event reporting
- serious adverse event (SAE) reporting
- ediary provision and training (all subjects)

Following completion of the day 1 visit assessments, eligibility, dry weight, and enrollment will be entered in the IVR/IWR system, as applicable. Following enrollment in the IVR/IWR system, IP will be dispensed and recorded on the day 1 eCRF.

CONFIDENTIAL

Page 46 of 79

